#### *Procedures*

Session	Orientation	Scan 1	Scan 2	Behav Session 1	Behav Session 2
Drug	Practice	MA*	PL*	PL*	MA*
Measures	MID Doors	Self-report Mood drug, cv	Self-report mood drug, cv	Self-report Mood drug, cv	Self-report mood drug, cv
	EEfRT	fMRI with MID, Doors and motor	fMRI with MID, Doors and motor	EEfRT	EEfRT
	Stop Task			Stop Task	Stop Task
	Simple reaction time			Simple reaction time	Simple reaction time
	Go-No-Go			Go-No-Go	Go-No-Go
	Continuous performance task gradCPT			Continuous performance task gradCPT	Continuous performance task gradCPT
	Weather Prediction Task			Weather Prediction Task	Weather Prediction Task
	Learning task			Learning task	Learning task

PL=placebo, MA=methamphetamine, \*orders counterbalanced

**(i) Imaging (2).** The two fMRI sessions will assess brain activity under the influence of MA and PL. After drug and pregnancy tests, we obtain baseline measures of mood, heart rate and blood pressure. At 9:15 am subjects ingest a capsule (PL or MA 20 mg) under double-blind conditions. The scan will be conducted from 60-120 min after ingestion of the capsule at the time of peak drug effect. During the scan subjects will complete the MID and the Doors task and have a resting state scan. We will obtain several indices of the effects of MA on reward circuit function: i) for reward anticipation: regional brain activation during the MID, MID task-related functional connectivity, ii) for reward receipt, regional brain activation during the Doors task, Doors task-related functional connectivity and iii) resting state functional connectivity. Subjects will also complete one other task assessing motor reactivity.

**(ii) Behavioral sessions (2):** Sessions are conducted from 9 am to 1 pm, at least 48 hours apart. Upon arrival drug and pregnancy tests are obtained, and subjects complete baseline measures of mood. Heart rate and blood pressure are measured. At 9:15 am they ingest capsules (PL or MA 20 mg, in color-coded capsules) under double-blind conditions. Oral MA (Desoxyn, 5 mg per tablet) will be placed in opaque size 00 capsules with dextrose filler. PL capsules will contain only dextrose. Subjects will complete mood and drug effects questionnaires at regular intervals, cognitive tasks and a learning task. At the end of the sessions subjects complete a questionnaire rating their overall drug experiences. The primary subjective measures during these sessions are ratings of drug liking and drug-induced euphoria. Secondary measures include cognitive tasks.

**(iv) End of study Interview** When subjects have completed both phases of the study the PI will fully inform subjects of the study aims and drugs administered.

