In this project, we will examine individual differences in the effects of a stimulant drug, methamphetamine (MA), on mesolimbic reward function using fMRI. We will determine how individual differences in neural activity after the drug are related to its behavioral, rewarding effects. The effects of MA on mesolimbic reward function will be examined using both reward-task-related activation and resting state functional connectivity. On separate sessions, we will examine the effects of MA on behavioral reward in the same subjects, using ratings of drug liking and euphoria, as well as measures of drug seeking (drug and dose choice). Our goal is to identify neural processes that predict MA liking and 'seeking' behaviors. We have preliminary evidence that amphetamine increases striatal brain activity during a nondrug reward task, and that it facilitates frontal-striatal resting state functional connectivity. We will extend these observations to a larger sample using a more sensitive task, more refined imaging techniques, more comprehensive behavioral assessment and sufficient power to compare men and women. Healthy young adults will first undergo two fMRI scans with placebo and MA (20 mg), while performing the Monetary Incentive Delay and the Doors task. Then, they will participate in two behavioral sessions conducted in our laboratory. We will examine correlations between the neural responses and behavioral responses to MA.

**Specific Aim 1. To determine the effects of MA on regional brain activity during anticipation of reward, task-related functional connectivity and resting state connectivity.** We will examine the direct effects of a moderate dose of MA (20 mg) vs placebo on mesolimbic circuits. Imaging measures will include on regional activation during two reward tasks, task-related changes in functional connectivity, and resting state functional connectivity. These measures of assess different dimensions of brain function impacting reward processing. We hypothesize that MA will increase activation in striatal regions during anticipation of reward, and enhance both task-related and resting state functional connectivity in fronto-striatal reward circuits. We also expect that there will be inter-subject variability in these effects.

[figure not shown]

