Participants will be healthy young men and women (N=80, 80). They will first participate two fMRI scans, when they receive oral MA (20 mg) and PL, in random order under double blind conditions. During the scan they will complete the Monetary Incentive Delay task (MID) (Knutson, Adams et al. 2001) and the Doors task (Carlson et al. 2011) and resting state data will be obtained. The primary outcome measures during these sessions will be task-related (anticipation and receipt of reward) regional brain activation, task-related connectivity, and resting state functional connectivity. After the two scans, subjects will participate in two behavioral sessions during which they receive MA (20 mg oral) or PL in mixed order, in color-coded capsules. Subjects will complete mood and drug effects questionnaires, and cognitive tasks.

**Subjects.** Healthy men and women aged 18-35 years will be recruited from the university and surrounding community without regard to race or ethnicity, according to Protocol 13681B. Initial

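### Behavioral-session capsules are color-coded although no described procedure or analysis uses the color, which weakens the blind for self-rated liking and gains nothing

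*Combined protocol and SAP*

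**What the plan says.** The color coding appears twice in the combined protocol and SAP. The Methods overview says "subjects will participate in two behavioral sessions during which they receive MA (20 mg oral) or PL in mixed order, in color-coded capsules". Procedures, item (ii), repeats it and claims a double blind in the same sentence: "At 9:15 am they ingest capsules (PL or MA 20 mg, in color-coded capsules) under double-blind conditions". The capsules themselves are then described: "Oral MA (Desoxyn, 5 mg per tablet) will be placed in opaque size 00 capsules with dextrose filler"; placebo capsules hold dextrose alone.

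The imaging sessions in Procedures, item (i), are worded differently, with no mention of color: "At 9:15 am subjects ingest a capsule (PL or MA 20 mg) under double-blind conditions".

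On outcomes, item (ii) states: "The primary subjective measures during these sessions are ratings of drug liking and drug-induced euphoria". On disclosure, item (iv) says that once both phases are complete "the PI will fully inform subjects of the study aims and drugs administered". The paragraph on mood effects adds ratings of liking and drug identification at a debriefing after the last session.

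Specific Aims lists, among the behavioral measures, "as well as measures of drug seeking (drug and dose choice". The Procedures table contains an orientation, two scans and two behavioral sessions, and no choice session.

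**The concern.** A color code has a clear use when subjects must later pick between capsules they have sampled. Without that step it is a visible feature that separates active drug from placebo, in sessions whose primary outcomes are self-ratings and so open to expectancy. The Consent section treats expectancy as a real threat: subjects are told that several drug classes, or placebo, are possible. A visible difference between the two capsules works against that precaution.

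At stake is the credibility of the methamphetamine-placebo contrast in liking and euphoria, which is also the behavioral side of Aim 2. The plan does not say how colors are assigned to drug and placebo, who holds the code, or whether the debriefing ratings come before the subject is told what was given.

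**Working it through.** The plan gives no figure on this point, so there is none to reproduce. The check is a comparison of sections, plus a count under each possible color assignment.

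**1. Does anything use the color?**

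| Place | Role of capsule color |
|---|---|
| Methods overview | Stated, no purpose given |
| Procedures table | None; no choice session |
| Procedures (i), imaging | Not mentioned |
| Procedures (ii), behavioral | Stated, no purpose given |
| Imaging tasks; cognitive and motor tasks | Not mentioned |
| Mood effects, including debriefing ratings | Not mentioned |
| C6 Statistical Plan | Not mentioned |
| Specific Aims | Not mentioned, but drug and dose choice is named, where color would have a use |

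The Procedures items also run from (ii) to (iv). Together with the choice wording in Specific Aims, this suggests that a phase was removed and the color coding stayed behind.

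**2. What does the color tell a subject within the study?** I read color-coded in its natural sense, that a subject's two capsules differ in color. The color does not name the drug. It does tell the subject that the second capsule is not the same as the first. A subject who felt a clear effect in the first session, or none, then has reason to expect something different in the second. With drug first, that lowers expectation for placebo; with placebo first, it raises expectation for drug. Both would widen the drug-placebo difference, so counterbalancing and the drug-order covariate need not remove it. This holds whether the pairing is fixed or varies by subject. Its size cannot be estimated from the document.

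**3. What could disclosure reveal about other subjects?** The sample is 80 + 80 = 160 (Methods).

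- One pairing for everyone: with two colors and two contents, one disclosure settles both pairings. At most 160 − 1 = 159 subjects remain, or 159/160 = 99.4%, which is 159 × 2 = 318 behavioral sessions. The number is smaller to the extent that subjects have already started or finished by then.
- Pairing randomized per subject: a disclosure says nothing about anyone else, so 0 of 160.

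The document neither states nor excludes either arrangement.

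**4. Can disclosure affect the subject who receives it?** Not in the session ratings, since it follows both phases. It could affect that subject's debriefing ratings of liking and drug identification if these are taken afterwards; the order is not stated.

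**The case against.** The strongest reply is that a color of unknown meaning reveals no drug. Subjects are told that several drug classes are possible, each behavioral treatment is taken once, and no color is mentioned for the scan capsules, so nothing lets a subject learn a color-effect link beforehand. This stands against any claim that the color is a drug label. It does not answer the narrower point that two different-looking capsules signal different contents.

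A reader might infer that the first disclosure unblinds staff for the rest of the trial, or that subjects from one university community will pass the code on. The document does not support this as a finding. It requires a single pairing for all subjects, which is nowhere stated, and nothing says that session staff attend the disclosure or that colors are discussed in it.

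A reader might also infer that Aim 2 is biased. That is not shown. The effects of interest in C6 are interactions of the neural drug effect with drug and time. An expectancy shift that is much the same in all subjects would enter the drug main effect instead, and nothing indicates that it would vary with neural response. Methods also calls the drug's mood and cardiovascular effects robust, so subjects have internal cues whatever the capsule looks like, and the added contribution of color is unknown.

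Finally, color could help subjects refer back to a capsule in the end-of-session and debriefing ratings. That is plausible, though the document does not say so, and session order does the same job without a visible difference.

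**Conclusion.** The point holds as a free improvement. The plan uses visibly coded capsules for drug and placebo in sessions it calls double-blind, gives the color no function, and collects its self-rated primary behavioral outcomes there. The within-subject cue exists under any color assignment, provided that a subject's two capsules do differ in color; its size is unknown. The cross-subject risk ranges from 0 of 160 (pairing randomized per subject) to an upper bound of 159 of 160 (one pairing for all). Actual unblinding and bias in Aim 2 remain possibilities that the document does not establish. Separately, the choice measures named in Specific Aims have no counterpart in Procedures, and the two need reconciling whatever is decided about color.

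**What to change.** - Delete the color coding from the Methods overview ("in mixed order, in color-coded capsules") and from Procedures (ii).
- State that drug and placebo capsules are opaque and identical in appearance, and are labeled only by subject and session.
- Use session order as the referent in the end-of-session and debriefing ratings.
- Reconcile the drug-choice wording in Specific Aims with Procedures: either remove it or describe the session that it refers to.
- If color is kept, state its purpose, randomize the color-drug pairing per subject, name the role that holds the code, and take the debriefing liking and drug-identification ratings before disclosure.

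The cost is one capsule color in place of two and a few changed sentences. Sample size, sessions and analyses are unaffected.

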### **Primary measures**

***Imaging:*** Scanning sessions will be conducted at least 48 h apart under the direction of [name] at the UC MRI Research Center (MRIRC) on a 3T Philips Ingenia scanner with a 32 channel headcoil. Subjects first complete a scanner safety questionnaire and baseline mood questionnaires.

Participants will be familiarized with the tasks before scanning, and once in the scanner, made comfortable and head stabilized with foam padding. We have observed no difference in head motion in association with a similar dose of d-amphetamine (unpublished data from Weafer et al (Weafer, Van Hedger et al. 2019)). Physiological sensors for heart rate and respiration will monitor patient status during scanning, and will be used in fMRI data analyses to account for physiological noise.

### ***Imaging tasks and data collection.***

***MID TASK:*** Following Knutson (Knutson, Adams et al. 2001), the MID task assesses neural responses for both reward anticipation and consumption, and offers actual small and large monetary gains and losses based upon performance. This optimized task version requires participants to respond rapidly during an individually determined response window. Response windows are titrated after a pre-scan practice and during imaging to ensure optimal performance, e.g., 50-80% success rates. There will be 2 runs consisting of 24 trials each. For each trial, a 500 ms anticipatory cue alerts the subject to the opportunity to either win money or avoid losing money, specified as +/- \$0.30 or \$3.00, or a neutral cue is given (\$0.0) indicating that no money is at stake. Win/avoid loss and \$0.30/\$3.00 are presented pseudorandomly and at equal frequency across 64 of the trials; 32 trials are the neutral cue condition interspersed with the other trials. After the cue there is a 2-4s (jittered) interval and then a stimulus (a white box) appears. The stimulus duration is derived from data collected during the pre-scan practice. Subjects are required to press their thumb button as quickly as possible while the stimulus is visible. Visual feedback is provided indicating whether the participant responded within the time frame. Pre-scan practice (PSP) assesses individual-specific reaction time (RT) for correct responses. PSP mean RT and standard deviation are used to calculate a response window for the stimulus cue during the first run of the MID inside the scanner. For example, a subject with a mean RT of 180ms and SD of 20 will have a stimulus duration/response window of 220ms (180+ 2\*20), and a delay jitter screen of 780ms (1000ms-220). The technician tracks performance after each run and uses the number of total correct responses to modify the response time for the next run. If a participant's accuracy falls below 50%, the stimulus duration/response window increases by 0.5 SD (and the delay jitter screen conversely). If the participant's accuracy exceeds 80%, then the stimulus duration/response window decreases by 0.5 SD. The subjects are told they will receive the money they win based on their performance, added to their payment for the scan. They cannot lose money, in accordance with the success rate calibration. The task takes ~20 minutes. For this study, cue conditions (receive/avoid losing \$0.30/\$3.00; or no

money at stake) primarily enhance subject task engagement and will be collapsed for primary analyses, in accordance with limited clear knowledge of neural system differences distinguishing such conditions (Oldham, Murawski et al. 2018).

**Doors Task.** Participants will complete the doors task (Carlson et al. 2011) during BOLD fMRI to assess brain activation during monetary reward and loss. Briefly, two doors are presented on the screen, and participants are told that behind one of the doors is a monetary prize of \$.50 (signaled by '↑') and behind the other door is a loss of \$.25 (signaled by '↓'). For each trial, participants are instructed to use a button box to choose one of the two doors. They are told that they will either win or lose money based on their choices, and that they had a chance of winning between \$0 and \$15 total based on their performance. In actuality, the subjects' performance has no impact on outcomes. The task consists of 30 predetermined Wins and 30 Losses presented in a pseudorandom order over two runs. The task requires 15 minutes to complete, and all subjects earn \$10.

**Motor task:** Subjects will complete a motor task to provide information on the effect of the drug on activation of brain regions controlling motor function. As in an early study from our laboratory Uftring (Uftring, Wachtel et al. 2001), subjects will complete a finger tapping task in which they touch their right thumb and index finger together repeatedly for three 20s blocks, alternating with 4 20s rest blocks. We will assess for motor system changes during this task.

The scan will include a 10-minute resting state sequence, eyes open fixating on a light crosshair on a dark background, a high-resolution T1-weighted image for alignment and spatial standardization, and an Arterial Spin Labeling sequence to assess blood flow (described below).

**Imaging data analysis.** Imaging data from fMRI tasks will be preprocessed and analyzed using AFNI tools, as in Van Hedger (Van Hedger, Keedy et al. 2018). Preprocessing steps include alignment of each time series, spatial registration of the aligned time series to the anatomical scan, anatomical scan warped to standard space and warp applied to functional data, functional data spatially smoothed, and intensity normalization. Neural activation for conditions of interest from each task will be estimated using AFNI's 3dDeconvolve program, incorporating motion and heart rate/respiration as regressors. For MID, we will use a gamma response function to create activation maps for each task element: cues, motor response, and feedback. For the secondary tasks, we will use block functions and create contrast maps between the two block types. Mean activation for each subject at each scan session will be extracted from regions of interest (ROI). For MID, ROIs will be 8mm spheres created around coordinates reported in a recent meta-analysis of 50 MID fMRI studies (Oldham, Murawski et al. 2018). For Cue: caudate, putamen ventral striatum, thalamus, and anterior insula; Feedback: ventromedial prefrontal, orbitofrontal cortex, ventral striatum, amygdala, and will be a subtraction of mean activation of loss trials from win trials in each ROI (this contrast is the most common and more sensitive approach, per Oldham); Motor: all prior ROIs (to confirm lack of drug effect), primary sensorimotor cortex. ROI activation will be a subtraction of mean activation of loss trials from win trials in each ROI (this contrast is the most common and more sensitive approach, per Oldham). We will also look specifically at win vs neutral and loss vs neutral to confirm whether findings are driven by sensitivity to reward or avoiding loss. Tapping: primary motor cortex: dorsal striatum (caudate, putamen). For connectivity analyses of the MID task and of resting state, we will use the CONN toolbox (Whitfield-Gabrieli and Nieto-Castanon 2012) which employs similar preprocessing steps (alignment and spatial standardization, intensity normalization, motion estimation, white matter and CSF-based regressors) implemented through SPM12. We will use a 2mm displacement cutoff. For MID task-related connectivity, we will conduct an ROI-to-ROI analysis, using the spherical masks described previously. The toolbox allows comparison of correlation strengths (Pearson r converted to Fisher z) of the timeseries between each pairing of the ROIs. We will compare these correlations between drug and placebo sessions, as well as extract ROI-to-ROI correlation values for assessment in relation to behavioral measures. For resting state, we will calculate seed-based connectivity maps separately for MA and placebo, as per our prior study (Weafer, Van Hedger et al. 2019). Seeds will be bilateral caudate, putamen, and ventral striatum. We will conduct paired t tests within CONN to compare connectivity following MA and placebo. As our hypotheses are specific to frontal and subcortical reward circuitry, statistical inferences will be made within an anatomically-focused frontal-insular-striatal partial brain mask. The mask will include medial and lateral frontal and orbital regions, bilateral precentral gyri, anterior and middle cingulate cortex, anterior insula and ventral striatum. Drug order will be included as a covariate in all analyses.

Arterial Spin Labeling (ASL) data will be preprocessed and analyzed using FSL analysis tools (Smith, Jenkinson et al. 2004). Quantification of CBF will be completed using FSL's BASIL tool (Chappell, Groves et al. 2009). CBF will be quantified in units of ml/100g/min using a kinetic model and defaults for the parameters consistent with recent consensus (Alsop, Detre et al. 2015). For the within group analysis between drug and PL, quantified CBF images will be normalized to MNI space and adjusted to account for individual differences in global CBF. We will assess for spatial overlap of significant changes in CBF and regions of interest from the fMRI outcomes to inform interpretation of our findings. If there are significant changes in CBF following methamphetamine, we will also include CBF as a covariate in each of our fMRI task-based and connectivity analyses.

**Mood Effects of Drug:** We will utilize standardized self-report questionnaires to assess the mood-altering effects of the drug during the scanning sessions (abbreviated questionnaires) and the behavioral sessions (Carter and Griffiths 2009). Participants will complete the Drug Effects Questionnaire (DEQ) (Morean, de Wit et al. 2013) which consists of 5 questions; "Do you feel any drug effect?", "Do you like the effects you are feeling now?", "Do you dislike the effects?", "Are you high?" and "Would you like more of what you consumed, right now?" each rated on a 100 mm visual analog scale. Ratings of liking will be one of our measures of mood effects of the drug. The Profile of Mood States (POMS) (McNair D. 1971), an adjective checklist, will be used to assess momentary mood states. Subjects indicate how they feel at the moment in relation to each of 72 adjectives on a 5-point scale from "not at all" (0) to "extremely" (4). The 72 adjectives form 8 scales: Anxiety, Depression, Anger, Vigor, Fatigue, Confusion, Friendliness, Elation. They will also complete the Addiction Center Research Inventory (ARCI) (Martin, Sloan et al. 1971), a 49-item true-false questionnaire that is sensitive to psychoactive drugs (Haertzen 1966), with scales measuring stimulant-like effects (Amphetamine; A, and Benzedrine Group; BG) and euphoria (Morphine-Benzedrine Group; MBG). The drug liking scale and the ARCI MBG scales will be the primary measures of positive mood effects of the drug. Subjects will also complete ratings of drug liking and drug identification during the debriefing session after the last session.

**Cardiovascular measures.** During sampling sessions we will measure heart rate and blood pressure at 30 min intervals using portable monitors (Omron 10 Plus, Omron Healthcare).

**Cognitive and Motor Tasks.** We will also obtain secondary measures of the effects of MA during sampling sessions. These will include standardized measures of attention and cognition, most of which are available on the public site Psychology Experiment Building Language; PEBL: Stop Task, Simple reaction time, Go-No-Go, continuous performance vigilance task, EEfRT), a simple finger tapping task and measures of reward and learning (Pessiglione et al, 2006; Jocham et al, 2014), and the Weather Prediction Task (WPT; PEBL)). The Stop Task and Go-No-Go assess inhibitory control, the simple reaction time and continuous performance tasks assess attentional control. The motor task measures psychomotor performance and fine motor speed, which may reflect effects of the drug independent of its rewarding effects. Individuals are instructed to tap the letter "A" on their keyboard with the index finger as rapidly as possible for eight trials of 10 seconds, once with the dominant hand and once with the non-dominant hand. Mean number of taps is the outcome measure. The EEfRT measures willingness to expend effort (number of key clicks) for varying amounts of reward (hypothetical money). The Gradual-Onset Continuous Performance Task (gradCPT; Esterman et al. 2013 Rosenberg et al. 2013) is a test of sustained attention and inhibitory control. Stimuli are grayscale images of cities and mountains. On each trial (800 ms), one image gradually transitions to the next using linear pixel-by-pixel interpolation. Participants are instructed to respond via button press to city scenes (90%) and to withhold response to mountains (10%). Performance is measured with response time variability and sensitivity ( $d'$ ). We will use two measures of simple reward learning, an instrumental approach and avoidance learning task used by Pessiglione and colleagues (Pessiglione et al., 2008; Fischer and Ullsperger, 2013) and the WPT, a standardized measure of learning. In the Pessiglione task subjects acquire associations between neutral symbols and either gain or loss of points.

